1.5 Handling of missing data

- As a general rule, missing data will not be imputed.
- In the analysis of the frequency qualitative variables, missing data will be handles as “unknown.” In the analysis of summary statistics of quantitative variables, missing data will be excluded.

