5.2.4 Occurrence of adverse drug reactions/infections by CTCAE Grade (the worst one)

(1) Analysis sets to be used

Safety analysis set, safety analysis set (Hodgkin’s lymphoma), and safety analysis set (anaplastic large-cell lymphoma)

(2) Data to be analyzed

For each data item, patients will be stratified into the following categories, and the type of adverse drug reactions, etc., will be analyzed:

Data item	Category
CTCAE Grade (the worst one)	≤Grade 2, ≥Grade 3, or unknown

The type of adverse drug reactions, etc., will be analyzed as follows:

Data item	Data to be analyzed
Type of adverse drug reactions, etc.	The incidence of adverse drug reactions, etc., for each CTCAE grade (the worst one) will be calculated by SOC and PT. For SOC, the number and percentage of patients with drug reactions, etc., will be calculated. For PT, the number and percentage of drug reactions, etc., will be calculated. SOCs will be presented in the internationally agreed order, and PTs will be presented in ascending order of HLGT and PT codes if their SOCs are “Investigations,” and in ascending order of PT code otherwise. The CTCAE grade (the worst one) is higher in the order of ≥Grade 3, ≤Grade 2, and unknown. If the same patient has multiple occurrences of the same adverse drug reaction, etc. (PT), the reaction with the highest CTCAE grade will be counted once per patient.

(3) Figure/table number

Tables 5.2.4-1 to 5.2.4-3

5.3 Percentage of patients with adverse drug reactions/infections by patient demographics and baseline characteristics and treatment given

(1) Analysis sets to be used

Safety analysis set, safety analysis set (Hodgkin’s lymphoma), and safety analysis set (anaplastic large-cell lymphoma)

(2) Data to be analyzed

For each data item, patients will be stratified into the following categories, and the percentage of patients with adverse drug reactions, etc. (with point estimate and 95% confidence interval) will be determined.

For categories associated and not associated with ranking, Fisher’s exact and Mann-Whitney U tests, respectively, will be used. If there is a category of “unknown,” it will be excluded to perform

the Mann-Whitney U test.

Data item	Category
Sex	Male or female
Age	<18 years, 18 to 64 years, 65 to 74 years, or ≥ 75 years
Disease duration	<1 year, <1 to 3 years, <3 to 5 years, ≥ 5 years, or unknown
ALK (for patients with anaplastic large-cell lymphoma)	Positive, negative, or unknown
Clinical stage	I, II, III, IV, or unknown

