B symptoms	Absent or present
ECOG Performance Status	0, 1, 2, 3, or 4
Past history of pulmonary disorders	Absent or present
Concurrent pulmonary disorders	Absent or present
Past history of malignant tumours	Absent or present
Concurrent malignant tumours	Absent or present
Concurrent hepatic disorders	Absent or present
Grade of hepatic disorder (Grade based on AST and ALT levels)	None, Grade 1, Grade 2, \geq Grade 3, or unknown
Concurrent renal disorders	Absent or present
Grade of renal disorder (Grade based on serum creatinine)	None, Grade 1, Grade 2, \geq Grade 3, or unknown
Weight	<40 kg, <40 to 50 kg, <50 to 60 kg, <60 to 70 kg, or ≥ 70 kg
BMI	<18.5 kg/m ² , <18.5 to 25 kg/m ² , <25 to 30 kg/m ² , or ≥ 30 kg/m ²
Smoking history	Never, current, past, or unknown
Prior drug therapy	Absent or present
Prior radiotherapy	Absent or present
Prior hematopoietic stem cell transplantation	Absent, present (autologous), present (homologous), present (autologous and homologous), or unknown
Initial dose of Adcetris	<1.2 mg/kg, 1.2 mg/kg, >1.2 mg/kg to <1.8 mg/kg, 1.8 mg/kg, or >1.8 mg/kg

Data item	Category
Mean dose of Adcetris	<1.2 mg/kg, 1.2 mg/kg, >1.2 mg/kg to <1.8 mg/kg, 1.8 mg/kg, or >1.8 mg/kg
Dose of Adcetris per 3 weeks	<1.2 mg/kg, 1.2 mg/kg, >1.2 mg/kg to <1.8 mg/kg, 1.8 mg/kg, or >1.8 mg/kg
Drug(s) other than Adcetris used for the treatment of the primary disease	Absent or present

(3) Figure/table number

Tables 5.3-1 to 5.3-3

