Patients will be stratified into the categories below and the incidence of infections considered related to Adcetris for each CTCAE grade (the worst one) will be calculated by presence or absence of drugs used for the prevention of infection, using Mann-Whitney U test. The CTCAE grade (the worst one) is higher in the order of Grades 5, 4, 3, 2, 1, and unknown. If the same patient has multiple occurrences of the same infection, the occurrence with the highest CTCAE grade will be counted once for the category.

Similar analyses will be performed by use or non-use of antibiotics/synthetic antibacterial agents or trimethoprim-sulfamethoxazole combinations and by use or non-use of trimethoprim-sulfamethoxazole combinations for bacterial infection, by use or non-use of antifungals for fungal infection, and by use or non-use of antivirals for viral infection.

For patients included in safety evaluation who use antivirals for the prevention of viral infection but experience viral infection, a list of the following items will be generated: patient number, viral infection (name of the infection), age, sex, diagnosis, past history of hematopoietic stem cell transplantation (autologous or homologous), and drugs used for the prevention of infection (antivirals). If the same patient has multiple viral infections, all these viral infections will be counted.

Data item	Category
CTCAE Grade (the worst one) of infections	None, Grade 1, Grade 2, Grade 3, Grade 4, Grade 5, or unknown

(3) Figure/table number

Tables 5.9.5-1 to 5.9.5-3 and 5.9.5-4

5.9.6 Occurrence of infections considered related to Adcetris by presence or absence of prior hematopoietic stem cell transplantation

(1) Analysis sets to be used

Patients included in safety evaluation and patients included in safety evaluation (Hodgkin’s lymphoma) or patients included in safety evaluation (anaplastic large-cell lymphoma)

(2) Data to be analyzed

The incidence of infections considered related to Adcetris for each CTCAE grade (the worst one) will be calculated by presence or absence of prior hematopoietic stem cell transplantation (absent, present [autologous], present [homologous], present [autologous and homologous], or unknown) using Kruskal-Wallis test. The grade category of “unknown” will be excluded from the test.

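### SAP 5.3, read literally, gives Fisher's exact test to ranked factors and the Mann-Whitney U test to unranked ones; the two test names appear to be reversed.

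*SAP*

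**What the plan says.** SAP 5.3 stratifies patients by each factor, reports the percentage with an adverse drug reaction and its 95% confidence interval, and then tests. The rule for choosing the test is "For categories associated and not associated with ranking, Fisher’s exact and Mann-Whitney U tests, respectively, will be used". The next sentence says "If there is a category of “unknown,” it will be excluded to perform" the Mann-Whitney U test. SAP 1.3 sets a two-sided 5% level.

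No list says which factors count as ranked. Prior hematopoietic stem cell transplantation (HSCT) has the levels "Absent, present (autologous), present (homologous), present (autologous and homologous), or unknown"; smoking history has "Never, current, past, or unknown".

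Other places that bear on intent:

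- SAP 5.9.5 analyses worst CTCAE grade of infection "by presence or absence of drugs used for the prevention of infection, using Mann-Whitney U test".
- SAP 5.9.6 compares the HSCT groups on the same ordered grade: "present [autologous and homologous], or unknown) using Kruskal-Wallis test". It adds: "The grade category of “unknown” will be excluded from the test".
- SAP 1.5 on missing data: "In the analysis of the frequency qualitative variables, missing data will be handles as" unknown.

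The Section 5.3 rule stands in the same words in the other two full SAP versions in the file. Neither supplemental SAP corrects it.

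**The concern.** The word *respectively* ties the first kind of category to the first test and the second kind to the second. Ranked factors therefore get Fisher's exact test, and unranked factors get Mann-Whitney.

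The outcome in 5.3 is binary: a patient either has a reaction or does not. Mann-Whitney can then work only by ranking the factor, comparing patients with and without a reaction on their factor level. For an unranked factor with three or more levels, those ranks are an accident of coding.

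A programmer or validator following the text would do two things. Prior HSCT would be tested for a trend along an order that has no meaning. Factors with a natural order, where a trend is the plausible signal, would get a test that ignores the order.

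**Working it through.** **1. Is the opposite pairing intended?** Three places suggest so. The exclusion of unknown values is stated only for Mann-Whitney, which suits an ordered scale in which unknown has no position. Section 5.9.5 applies Mann-Whitney to ordered grade. Section 5.9.6 treats the HSCT groups as unordered (Kruskal-Wallis ignores group order), whereas literal 5.3 would order those same groups. The two sentences in 5.3 do not strictly contradict each other, because ALK, smoking history and HSCT also carry an unknown level.

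**2. Which factors are affected?** My classification of the 25 factors in 5.3:

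| Type | Factors | Number |
|---|---|---|
| Ordered | age, disease duration, stage, ECOG PS, hepatic grade, renal grade, weight, BMI, three dose items | 11 |
| Two-level | sex, ALK, B symptoms and the absent/present items | 12 |
| Unordered, more than two levels | prior HSCT, smoking history | 2 |

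There are three analysis sets, and ALK applies only to anaplastic large-cell lymphoma, so there are at most 24 × 3 + 1 = 73 distinct tests: 33 ordered, 34 two-level and 6 unordered. If smoking is treated as ordered, the split is 36, 34 and 3.

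**3. Effect on prior HSCT.** The documents give no counts, so every table and rate below is assumed. Take N = 140, with 70/42/17/11 patients in the listed order (absent, autologous, homologous, both) and 38/34/8/8 with a reaction, so m = 88 with and k = 52 without.

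- Mid-rank of a level = patients in the levels before it + (n + 1)/2: 35.5, 91.5, 121, 135.
- Rank sum W = 38×35.5 + 34×91.5 + 8×121 + 8×135 = 6508. Expected m(N + 1)/2 = 88×141/2 = 6204.
- Tie term Σ(n³ − n) = 342,930 + 74,046 + 4,896 + 1,320 = 423,192.
- Variance = (mk/12)[(N + 1) − tie term/(N(N − 1))] = (88×52/12)(141 − 423,192/19,460) = 45,475; SD 213.2.
- z = (6508 − 6204)/213.2 = 1.43, p = 0.154.

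The 24 orders of the levels give 12 distinct p-values, because reversing an order changes nothing. They run from 0.0017 to 0.476, and 7 are below 0.05. The exact Fisher (Freeman-Halton) test gives 0.0126 whatever the order.

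That table zig-zags (54%, 81%, 47%, 73%), which is hard on a rank test. Other assumed tables, by the same formulas:

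| Pattern | Reactions / patients | Mann-Whitney, listed order | Range over orders | Fisher |
|---|---|---|---|---|
| Autologous higher | 40/70, 33/42, 10/17, 7/11 | 0.238 | 0.030 to 0.255 | 0.117 |
| Homologous higher | 40/70, 25/42, 16/17, 8/11 | 0.035 | 0.021 to 0.774 | 0.021 |
| All transplanted higher | 38/70, 31/42, 13/17, 8/11 | 0.020 | 0.017 to 0.728 | 0.113 |
| Smoking (never, current, past) | 40/60, 26/32, 28/48 | 0.458 | 0.038 to 0.458 | 0.097 |
| Two-level factor | 52/80, 48/60 | 0.053 | 0.053 | 0.060 |

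Mann-Whitney is not always the weaker test: with all transplanted groups higher, its p-value is the smaller one. Two-level factors barely change.

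**4. Power and error rate (simulation, two-sided 5%).**

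| Scenario | N | Mann-Whitney | Fisher |
|---|---|---|---|
| HSCT at the first table's rates, listed order | 140 | 30% | 81% |
| same | 90 | 21% | 60% |
| same | 40 | 11% | 29% |
| HSCT, no difference (63% throughout) | 140 | 5.0% | 4.7% |
| ECOG trend 55/65/75/85/92% | 140 | 77% | 54% |
| same | 90 | 56% | 29% |
| same | 50 | 34% | 12% |
| same | 35 | 25% | 8% |
| Ordered, non-monotone 85/60/80/90% | 140 | 4% | 76% |

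A repeat simulation at N = 140 gave about 31% v 79% for HSCT and 74% v 52% for the ECOG trend, so read these as good to a few points. With one fixed coding the literal rule keeps its 5% error rate.

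**5. Unknown values.** The text excludes unknown only for Mann-Whitney. Whether Fisher's test keeps it as a level is not stated, although the wording suggests so. Adding an unknown level to the first HSCT table (2/3, 5/7 or 7/10 with a reaction) moves Fisher's p from 0.013 to 0.022, 0.025 or 0.026.

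**The case against.** The strongest reply is that this is a word-order or translation slip in a text with other slips, that intent is clear from context, and that little depends on it. The protocol (Section 10.4.2) asks only for frequencies by factor. Percentages and intervals are unaffected, and no sample-size statement or decision rule uses these p-values. Fisher's test on an ordered factor is valid, and the non-monotone row above shows it can be much the better one. The sizes all come from assumed tables, the lead one unfavourable to a rank test. The range over all orders also overstates the doubt, since the SAP lists a single order. Finally, 5.9.5 places unknown grade below Grade 1 and states no exclusion for its own Mann-Whitney test, so the SAP does not drop unknown consistently.

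Most of this stands as a limit on size. The loss for ordered factors is one of sensitivity to a monotone trend, not of validity, and the argument from the handling of unknown is suggestive rather than conclusive. It does not remove the point: the sentence is the written instruction, it is repeated in every full SAP version in the file, and for an unordered factor with more than two levels it names an unsuitable test. A slip that readers must correct in their heads still needs correcting in the plan.

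**Conclusion.** The concern holds. As written, the test assignment in SAP 5.3 is the wrong way round, and the SAP's other rank tests support the opposite pairing. It should be fixed, but the reach is narrow. The clear error affects one or two of 25 factors, a further 11 lose sensitivity to trend, and 12 hardly change. The harm is a poorly aimed exploratory test, not inflated false positives, and it arises only if the program followed the sentence, which the documents do not show. The illustrative sizes rest on assumed counts and rates; the reading of the text does not.

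**What to change.** Exchange the two test names: Mann-Whitney U, with unknown excluded, for ordered categories; Fisher's exact test for unordered ones. List the factors treated as ordered, and say whether smoking history is among them. State whether unknown is a level or is excluded in Fisher's test for ALK, smoking and HSCT, since SAP 1.5 turns missing values into that category. Then check the program, and rerun Tables 5.3-1 to 5.3-3 only if it followed the literal sentence.

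The cost is one corrected sentence, a short list, one line on unknown values and a program check, with no new data. The trade-off is that the rank test can miss a non-monotone pattern, so the per-category percentages and confidence intervals should be read alongside it.

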## 3.0 Estimated Enrollment and Its Rationale

### 3.1 Estimated enrollment

140 patients (with relapsed/refractory CD30+ Hodgkin's lymphoma or anaplastic large cell lymphoma)

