### 3.2 Rationale

It is expected that the detailed evaluation of peripheral nerve disorders, infections, neutropenia, infusion reactions, and pulmonary disorders will help better understand the safety profile of Adcetris in the routine clinical setting, which will lead to the assessment of the risk-benefit balance of the drug.

The frequencies of peripheral nerve disorders, infections, neutropenia ( $\geq$ Grade 3), infusion reaction, and pulmonary disorder in non-Japanese phase 2 studies (pooled study data from a study in patients with Hodgkin's lymphoma [SG035-0003, 102 patients] and a study in patients with systemic anaplastic large cell lymphoma [SG035-0004, 58 patients]) were 56%, 61%, 20%, 11%, and 6%, respectively.

Observation of infusion reactions with the lowest frequency of  $\geq 10$  patients, aside from pulmonary disorders, with a probability of 95% would require 140 patients, which was therefore determined to be the estimated enrollment. It is estimated that when the number of patients enrolled reaches 140 patients,  $\geq 4$  patients have adverse events of pulmonary disorder with a probability of 95%.

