1.3 Level of significance and confidence coefficient

Level of significance: Two-sided 5%

Confidence coefficient: Two-sided 95%

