3.0 Patient Demographics and Baseline Characteristics

3.1 Patient Demographics and Baseline Characteristics

(1) Analysis sets to be used

Safety analysis set, safety analysis set (Hodgkin’s lymphoma), and safety analysis set (anaplastic large-cell lymphoma)

(2) Data to be analyzed

For each data item, patients will be stratified into the categories below, and the frequency will be calculated. In addition, summary statistics of continuous variable will be calculated:

Data item	Category
Sex	Male or female
Age	<18 years, 18 to 39 years, 40 to 64 years, 65 to 74 years, or ≥75 years
	<18 years, 18 to 64 years, 65 to 74 years, or ≥75 years
Disease duration	<1 year, <1 to 3 years, <3 to 5years, ≥5 years, or unknown
Diagnosis	Hodgkin’s or anaplastic large-cell lymphoma or other
Status	Relapsed/refractory, or new-onset
CD30	Positive, negative, or not measured
Site(s) of involvement	Lymph node, spleen, liver, lung, bone, central nerve, bone marrow, skin, and/or other
ALK (for patients with anaplastic large-cell lymphoma)	Positive, negative, or unknown
Clinical stage	I, II, III, IV, or unknown
B symptoms	Absent or present
ECOG Performance Status	0, 1, 2, 3, or 4
Therapeutic category	Outpatient, inpatient, or unknown
Hypersensitivity disposition	Absent, present, or unknown
Specific hypersensitivity disposition(s)	Medications, food allergy, and/or other
HCV antibody	Negative, positive, or unknown
HBs antigen	Negative, positive, or unknown
HBs antibody	Negative, positive, or unknown
HBV DNA	Negative, positive, or unknown
Past history of pulmonary disorders	Absent or present
Concurrent pulmonary disorders	Absent or present

Data item	Category
Past history of malignant tumours	Absent or present
Concurrent malignant tumours	Absent or present
Past history (other than pulmonary disorders and malignant tumours)	Absent, present, or unknown
Concurrent illness (other than pulmonary disorders and malignant tumours)	Absent or present
Specific concurrent illness(es) (other than pulmonary disorders and malignant tumours)	Diabetes mellitus, hypertension, dyslipidaemia, hyperuricaemia, hepatic disease(s), renal disease(s), infections, peripheral nerve disorders, and/or other
Past history (other than pulmonary disorders and malignant tumours)	Absent, present, or unknown
Concurrent hepatic disorders	Absent or present
Grade of hepatic disorder (Grade based on AST and ALT levels)	None, Grade 1, Grade 2, \geq Grade 3, or unknown
Concurrent renal disorders	Absent or present

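### SAP 5.3 tests age in four classes with all adults aged 18 to 64 tied, although age in years is available; a test on recorded age would avoid a moderate, assumption-dependent loss of power

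*SAP*

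**What the plan says.** SAP 5.3 stratifies patients by each background or treatment factor and gives, per class, the percentage with an adverse drug reaction and its 95% confidence interval. It then attaches a test to the classes, in a rule that begins "For categories associated and not associated with ranking". Age has four classes: "<18 years, 18 to 64 years, 65 to 74 years" and 75 and over. Weight has five, printed as "<40 kg, <40 to 50 kg, <50 to 60 kg, <60 to 70 kg" and 70 kg or more. BMI and disease duration have four each, apart from unknown duration. No test on the underlying number is planned.

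The numbers exist. The Protocol collects date of birth (9.1), and height, weight and date of diagnosis (9.2.2). The SAP's definitions derive age in whole years, BMI, and disease duration in years, with the day of diagnosis set to the first of the month. SAP 3.1 asks for summary statistics of continuous variables and has a finer age grouping that includes "18 to 39 years, 40 to 64 years".

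SAP 1.3 sets the level ("Level of significance: Two-sided 5" per cent). Protocol 10.4.2 asks for adverse event frequency by background factors. It lists age, but not weight, BMI or disease duration, and it specifies no test.

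**The concern.** A Mann-Whitney test ranks raw values and needs no classes. Putting everyone from 18 to 64 into one class turns most of the age range into a single tie, probably covering most of the patients. If the risk of a reaction rises or falls steadily across adult life, the test cannot see any of that change below 65. SAP 5.3 is the only section that tests age, weight, BMI or disease duration; 5.9.2 tabulates peripheral nerve disorders by several such factors without a test. A real age trend could therefore be reported as non-significant more often than the data require. The same tests are repeated in the smaller Hodgkin's and anaplastic large cell lymphoma sets, where there is less information to spare.

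**Working it through.** **The plan's own figure.** Protocol 3.2 gives frequencies that "were 56%, 61%, 20%, 11%, and 6%, respectively", of which 11% is infusion reaction and 6% pulmonary disorder. It says that seeing at least 10 infusion-reaction patients "with a probability of 95% would require 140 patients". With exact binomial tails, P(X ≥ 10 | n = 140, p = 0.11) = 0.952, and 140 is the smallest n that reaches 0.95. P(X ≥ 4 | n = 140, p = 0.06) = 0.971. The figure reproduces. It is a detection target, so there is no stated power for 5.3 to compare with.

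**Inputs from the documents.** n = 140; two-sided 5%; age cuts at 18, 65 and 75; weight cuts at 40, 50, 60 and 70 kg; BMI cuts at 18.5, 25 and 30; duration cuts at 1, 3 and 5 years.

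**Assumptions, not in the documents.** Age mix, reaction rate and effect size, and the distributions of weight (mean 57, SD 11), BMI (mean 21.5, SD 3.3) and duration (log-normal, median 2 years).

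**Method.** Simulate logit P(reaction) = a + b·z, where z is the factor in SD units. Apply the Mann-Whitney test, patients with versus without a reaction, to the recorded value and to the SAP class. Relative loss = 1 − power(classes) / power(recorded). With 4,000 runs per main age setting, the Monte Carlo standard error is at most √(0.25/4000) = 0.008.

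**Age, steady trend.** Rows 1 to 4 use an odds ratio of 1.8 per SD (b = ln 1.8 = 0.59) and the overall reaction rate. Their mixes are shares in the four SAP classes. Rows 5 to 9 use b = 0.6 and the reaction rate at mean age.

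| Age mix | Reaction rate | Recorded age | Four classes | Relative loss |
|---|---|---|---|---|
| 2/60/22/16% | 80% | 0.762 | 0.596 | 22% |
| 2/75/14/9% | 80% | 0.750 | 0.464 | 38% |
| 2/60/22/16% | 60% | 0.908 | 0.786 | 13% |
| 2/75/14/9% | 60% | 0.907 | 0.701 | 23% |
| mean 60, SD 16 | 80% | 0.795 | 0.602 | 24% |
| mean 55, SD 18 | 80% | 0.789 | 0.577 | 27% |
| mean 45, SD 18 | 80% | 0.770 | 0.542 | 30% |
| mean 55, SD 18 | 60% | 0.910 | 0.763 | 16% |
| mean 45, SD 18 | 90% | 0.546 | 0.326 | 40% |

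Over all settings tried, the loss ran from about 4% to 42%. Under no effect, rejection was 0.048 to 0.055 on recorded age and 0.050 to 0.055 on classes, so grouping buys no extra error control.

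**Adding the split at 40** (80%, b = 0.6; 1,000 runs, recorded age re-simulated). Power is 0.727 against 0.777 on recorded age (mean 55), 0.725 against 0.770 (mean 45) and 0.735 against 0.770 (mean 60), a loss of 5% to 6%. The squared rank correlation between age and class rises from 0.49–0.75 to 0.85–0.86.

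**Other variables** (80%, b = 0.6). BMI 0.789 to 0.678 (14%); weight 0.773 to 0.739 (4%); duration 0.782 to 0.734 (6%). Over all settings, BMI lost 2% to 19%, and weight and duration at most about 8%.

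**Risk that steps up at 65** (70% below 65, log-odds 1.2 higher from 65). Power on recorded age against classes is 0.453 against 0.625 (mean 55), 0.160 against 0.265 (mean 45) and 0.575 against 0.719 (mean 60). Here the classes win.

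**The case against.** The strongest case on the other side has four parts.

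First, the loss depends on the shape of the age effect. A step at 65 reverses the comparison, and the documents say nothing about shape. This stands, and it must be stated as the downside of the change. It does not cancel the point, because the retained class percentages and intervals would still display a step at 65, whereas nothing in 5.3 displays a trend below 65. A step placed at 50 also loses power under the SAP classes.

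Second, the four age groups serve the plan: SAP 5.4 and 5.9.2 use them too, and the 5.3 test belongs to the table of classes. This also stands. It is why the test on age in years should be reported with the table and labelled as such, and why the table should stay.

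Third, 5.3 is an unadjusted screen of more than 20 items in three analysis sets, with no planned power. This stands and limits how much the point matters.

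Fourth, read literally, 5.3 gives ranked classes Fisher's exact test, so the Mann-Whitney comparison is not the one the text assigns to age. The comparison above holds the test fixed to isolate the effect of grouping. The assignment needs its own correction, and its extra loss is not counted here.

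**Conclusion.** The point holds as a modest one about age. SAP 5.3 discards information that the SAP itself derives and that its section 3.1 partly keeps. Under a steady trend, the typical relative loss of Mann-Whitney power from grouping alone is about 10% to 40% for age. It is smaller for BMI and small for weight and disease duration. Every figure rests on assumed age mix, reaction rate and effect size.

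A reader might infer that 5.3 loses a third or more of its power across all four variables. The documents do not support that. They give no inputs from which a loss could be derived, a third is reached only for age and only in some assumed settings (one of the first four rows), and weight and disease duration are barely affected. Nor is exact duration available, since diagnosis is dated only to the month. A reader might also infer that the study falls short of a planned power or that the 5.3 tables are wrong. Neither follows: 140 comes from a detection target that reproduces, and type I error is near 5% either way.

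**What to change.** Keep the 5.3 table of classes with percentages and 95% confidence intervals. Add one sentence: for age, and likewise BMI, weight and disease duration (known to the month), a Mann-Whitney U test on the recorded or derived value, comparing patients with and without an adverse drug reaction, is reported with the table and labelled as a test on the value. If a class-based p value is also printed, say beforehand which one is to be read. At minimum, replace the 18 to 64 class in 5.3 by the two classes of SAP 3.1.

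The cost is one sentence and a change of input variable in the program. No new data are needed, and with the first option the tabulated percentages do not change; the minimum option adds one age row. The price in power is a weaker test if risk changes only at 65. Correct the Fisher and Mann-Whitney assignment in the same paragraph as a separate item.
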